3.4.4 Subgroup analyses

All subgroups will be defined by the presence or absence of a pre-randomization variable, we will not select any subgroups based on post-randomization events.^{4,5}

The primary outcome for planned subgroup analyses will be the same as in the main analysis, i.e. 90 day all-cause mortality. Most subgroup analyses will be exploratory and aim at generating new hypotheses although for the first two subgroup analyses described below we are seeking to examine the presence of the interaction inferred from the results of Van den Berghe studies.^{1,2,6} Unadjusted p-values will be reported but the number of declared subgroups analyses will be specified in all publications.

Analysis

The main analysis for each subgroup will be an unadjusted test of interaction in a logistic model to determine whether the effect of treatment differs significantly across categories, e.g. in patients with sepsis versus those without sepsis. The number of deaths over total number of participants per arm, the treatment effect (odds-ratio) and its confidence interval for each category within each subgroup will be presented along with the p-value for the interaction test. Where appropriate, analyses considering continuous variables will also be performed, in that case only the interaction test will be reported.

The following status *at baseline* specifies the 6 subgroup analyses:

1. operative patients versus non-operative patients
2. patients with diabetes mellitus versus those without
3. patients with severe sepsis versus those without
4. patients diagnosed with trauma versus those without
5. APACHE II score of 25 or more versus APACHE II score of less than 25
6. patients treated with corticosteroids versus those not treated

Rationale

The rationale for considering these subgroup is as follows:

1. Contrasting evidence in two large trials conducted by Van den Berghe and colleagues, the first in surgical (SICU) patients and the second in medical (MICU) patients.^{1,2} A significant reduction in the relative risk of death was found in the intention-to-treat population of the SICU trial but not in the MICU study.
2. In a publication combining the results of their MICU and SICU studies, Van den Berghe and colleagues identified patients with diabetes as a subgroup who did not benefit from normalization of blood glucose.⁶
3. Conflicting signals in patients with sepsis versus those without. In Van den Berghe and colleagues' SICU trial, the excess mortality was attributed to deaths from sepsis.¹ In Van den Berghe and colleagues' MICU trial, the authors claimed that deaths from all causes were reduced.² Hyperglycaemia is thought to impair white blood cell function and so may theoretically reduce a person's ability to deal with infections. Despite the potentially beneficial effects of IIT in patients with severe sepsis, a trial of IIT conducted by the German Sepsis Network was stopped early due to safety concerns in the absence of a beneficial treatment effect.⁷

4. Patients admitted to the ICU because of trauma have a very different demographic profile to other ICU patients. They are younger and have less co-morbidity. The mortality rate of trauma patients without traumatic brain injury is much lower than the general ICU population but a recent publication by Vogelzang et al. reported that the association between hyperglycaemia and adverse outcome was stronger in trauma patients than in other critically ill patients.⁸

5. The NICE-SUGAR patients represent a heterogeneous population treated in ICUs (diagnoses, severity of disease). A criticism of Van den Berghe's studies has been that the patients had a low severity of illness as assessed by the APACHE II score and inappropriately high mortality. In addition, some treatments may be beneficial in ICU patients with higher risk of death as assessed the APACHE II score or similar tools.^{9, 10}

6. Following the publication of Annane's study in 2002,¹¹ corticosteroids have been used to treat critically ill patients with increasing frequency and were being received at time of randomization by over 50% of patients in Van den Berghe's MICU study.² Corticosteroid therapy increases glucose intolerance and could theoretically influence the treatment effect of intensive insulin therapy.

Presentation of results

Subgroup results for categorical variables will be presented as Forrest plots - with p-values for heterogeneity for each pair of subgroups.

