1.4 Analysis principles

1. All analyses will be conducted on an intention-to-treat basis.
2. All tests are two-sided and the nominal level of α will be 5%.
3. All statistical analyses will be unadjusted except where indicated.
4. Subgroup analyses will be carried out irrespective of whether there is a significant effect of treatment on the primary outcome.
5. We will not impute missing values unless specified otherwise. Where the number of missing observations is substantial, we will report the number of observations used in the analysis. Last observations will not be carried forward for continuous outcomes, e.g. the SOFA scores.
6. P-values will not be adjusted for multiplicity. However the outcomes are clearly categorized by degree of importance (primary to tertiary) and a limited number of subgroup analyses are pre-specified.

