2.3 Treatment allocation

Eligible patients will be randomized to one of the two blood glucose targets using minimization. Two strata will be considered: the type of critical illness (post-operative versus non-operative) and geographic region (Australia and New Zealand versus North America). Centralized randomization will be achieved via a password-protected web-based program.

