2.4 Power

We plan to enrol 6100 patients providing 90% power to detect an absolute decrease in mortality of 3.8% from a baseline of 30% (two-sided alpha <0.05). The study is powered to detect a relative risk reduction of 12.7%, which is 37% of the treatment effect documented in Van den Berghe's first study,¹ this difference is clinically important and if detected would likely lead to widespread change in the practice of glycemetic control in ICU's in Australia, New Zealand, North America and beyond.

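### The continuous APACHE II interaction, planned beside a main test that cuts the score at 25, would be reported as a p-value without estimate or confidence interval

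*SAP*

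**What the plan says.** SAP section 3.4.4 makes an unadjusted logistic interaction test across categories the main analysis of every subgroup. On the endpoint it says: "The primary outcome for planned subgroup analyses will be the same as in the main analysis, i.e. 90 day all-cause mortality". The fifth of the six subgroups is "APACHE II score of 25 or more versus APACHE II score of less than 25".

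For each category the section promises deaths and denominators by arm, an odds ratio with its confidence interval, and the interaction p-value. A forest plot follows (sections 3.4.4 and 3.6).

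Continuous analyses are covered by one sentence: "Where appropriate, analyses considering continuous variables will also be performed, in that case only the interaction test will be reported". It names no variable and no functional form.

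The section describes most subgroup analyses as exploratory. Only the first two, operative status and diabetes, are meant to examine an interaction suggested by earlier trials. The rationale for the fifth concerns varied severity and possible benefit in patients at higher risk of death. It gives no reason for choosing 25.

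**The concern.** The rationale asks a graded question: does the treatment effect change as risk of death rises? The model that uses the whole score addresses this most directly, yet the plan reduces its output to a p-value. That has three consequences:

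- A p-value alone does not show whether the effect grows or shrinks with severity, or by how much.
- Without an interval, a non-significant result cannot show which interactions are ruled out.
- If the continuous test and the split disagree, the reader cannot see why.

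The continuous analysis is also conditional on being judged appropriate, with no criterion given, so the decision to run it could be taken after the data are seen. Meanwhile the designated main test uses only which side of 25 a patient falls on, which costs information if the effect changes gradually.

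**Working it through.** **1. The plan's own figure.** Section 2.4 says: "We plan to enrol 6100 patients providing 90% power". The design is 30% versus 26.2% mortality, with a two-sided 5% level (section 1.4). The allocation ratio is not stated in section 2.3, so 1:1 is assumed, giving 3050 per arm.

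- Relative reduction: 3.8/30 = 12.67%, which matches the stated 12.7%.
- Mean proportion: 0.281. Null SD term: √(2 × 0.281 × 0.719) = 0.6357. Alternative SD term: √(0.30 × 0.70 + 0.262 × 0.738) = 0.6351.
- Power: Φ[(0.038 × √3050 − 1.96 × 0.6357)/0.6351] = Φ(1.34) = 91.0%.
- Total N for 90% power: 5878 without continuity correction, 5982 with it.

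The main design therefore reproduces. The SAP states no power for any subgroup interaction, so there is no subgroup figure to reproduce.

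**2. Information kept by a cut, if the interaction is linear in a normal score.** With a share p of patients at or above the cut, c the normal quantile at 1 − p, and φ the normal density, relative efficiency is φ(c)²/[p(1 − p)]. If the continuous test has 80% power, the cut has power Φ[(1.96 + 0.8416) × √efficiency − 1.96].

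| Share at 25 or more (assumed) | Efficiency of the cut | Power of the cut when the continuous test has 80% |
|---|---|---|
| 50% | 0.637 | 61% |
| 40% | 0.622 | 60% |
| 30% | 0.576 | 57% |
| 20% | 0.490 | 50% |

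Example at 30%: 2.8016 × √0.576 = 2.126, and Φ(2.126 − 1.96) = 57%.

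**3. Check in the logistic model itself.** Expected information was computed for N = 6100 and 30% control mortality. Assumptions not in the SAP: APACHE II roughly normal with mean 18-25 and SD 7-8 (21-53% at 25 or more), and a prognostic log-odds of 0.7-0.9 per SD. The interaction giving the continuous test 80% power is a ratio of odds ratios of about 1.20-1.22 per SD. With SD 8 this is 1.20^(5/8) to 1.22^(5/8), or about 1.12-1.13 per 5 points. The cut at 25 then has efficiency 0.53-0.61 and power of about 53-59%.

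**4. Simulation.** There were 400 trials per scenario, with 6100 patients, mean 21, SD 8, about 28% mortality and a linear interaction. Power for the continuous test versus the split was 84% versus 64%, 63% versus 43%, and 41% versus 27%. Both rejected about 4% of the time under no interaction. Monte Carlo error on a power figure is at most √(0.25/400) = 2.5 points.

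**5. Counter-case.** If the effect is a step exactly at 25 (mean 21, SD 8), a ratio of odds ratios of about 1.41 across the cut gives the split 80% power. The linear term then has about 62%, so the ranking reverses.

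**6. What the reader would see.** The split yields two odds ratios with CIs and an interaction p-value. The continuous model, if run, yields a p-value only.

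**The case against.** A reader might infer that the plan reports no size or direction of effect modification by severity. The document does not support that: section 3.4.4 gives an odds ratio and CI on each side of 25, and the forest plot displays them. Nor has the plan simply given up power, because it foresees a continuous test beside the split. The continuous test is the stronger one only under a roughly linear interaction. The SAP does not say what shape is expected, and the simulations in step 4 impose linearity.

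The remaining objections are also fair. The sentence on continuous analyses does not name APACHE II, so the link is an inference. The efficiency figures rest on an assumed score distribution. A pre-specified cut with an odds ratio on each side is a transparent choice that follows one rule for all six subgroups. The subgroup is exploratory.

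All of this stands, and it rules out calling the split an error or insisting that it lose its place as the main test. It does not justify the reporting rule. Two odds ratios either side of 25 give one contrast, not a trend, and they do not supply the estimate or precision of the continuous interaction. Exploratory work needs estimates more than p-values, and withholding this one has no statistical benefit.

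**Conclusion.** The point holds as a minor reporting gap. As written, the continuous APACHE II analysis is not firmly committed to and, if run, would be published without size, direction or interval.

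Under a roughly linear interaction and a roughly normal score with 20-50% of patients at 25 or more, the split keeps about 50-64% of the information. Power of 80% on the continuous score then corresponds to about 50-61% on the split. Under a true step at 25 the split is the better test, so reporting both with estimates is the sound course. A reader might go further and conclude that the cut is wrong or that the severity question cannot be answered. The category odds ratios and the foreseen continuous test do not support that. The primary analysis and the trial's main conclusion are unaffected.

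**What to change.** In section 3.4.4:

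- Name APACHE II as the variable to be analysed continuously, and commit to a logistic model with treatment, the score as a linear term, and their interaction, beside the split at 25.
- Replace the test-only rule with the interaction estimate (ratio of odds ratios per 5 points), its 95% CI and p-value.
- Add a plot of the treatment odds ratio against the score. A flexible curve, with its form fixed in advance and the linear fit laid over it, would let the plot show departures from linearity.
- Keep the split at 25 and its forest-plot row. Making the continuous interaction the main test for this subgroup is optional.

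The cost is a change of wording, one more model output and one figure. No new data are needed, since APACHE II is already collected at baseline (section 2.1). The downside is the assumption of rough linearity, which the plot and the retained split help to check.

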3.5 Control of type I error for multiples looks

The Peto rule with a maximum of 3 analyses will be used to decide on early stopping. The last critical value is $c_3=1.975$ if the trial goes to completion and the 3 interim analyses are equally spaced. This value will be recalculated if more interim analyses are considered or they are not roughly equally spaced. Although naïve estimates obtained after stopping a trial earlier can theoretically be slightly biased we will not correct the estimates on termination as bias is likely to be negligible with this design. However, to be conservative, we will report repeated CI's at each interim analysis - if required by the DSMB - or on termination. As a result, the critical value used to compute the last CI should be 1.975 as opposed to the classical 1.96. This will hold for the primary and secondary analyses.

3.6 Tables and figures

Tables include baseline characteristics of the participants, process measures and concomitant treatments – time on treatment algorithm, number of patients treated with insulin and amount of insulin administered, blood glucose concentration, treatment with corticosteroids, non-protein calories administered and route, outcomes including safety outcomes and subgroup analyses. The content and proposed formatting is displayed in the spreadsheet attached to this document.

Planned figures are:

1. A CONSORT diagram illustrating flow of patients through the study
2. Bar graphs for mean (SD) total non-protein kilocalories administered and mean (SD) non-protein kilocalories administered by enteral route per day by treatment arm for the first 14 days (2 plots), and mean (SD) time-weighted blood glucose concentration on study treatment by treatment group for the first 14 days (3rd plot)
3. A Forrest plot of odds ratios for death at 90 days for all patients and for *a priori* subgroups as described in III 3.4.
4. A Kaplan Meier curve for survival to 90 days

